13 PROTOCOL VIOLATIONS

A protocol violation occurs when the participant, investigator, or Sponsor fails to adhere to significant protocol requirements affecting the inclusion, exclusion, participant safety and primary endpoint criteria. Protocol violations for this study include, but are not limited to, the following:

- Failure to meet inclusion/exclusion criteria

Failure to comply with Good Clinical Practice (GCP) guidelines will also result in a protocol violation. The Sponsor will determine if a protocol violation will result in withdrawal of a participant.

When a protocol violation occurs, it will be discussed with the investigator and a Protocol Violation Form detailing the violation will be generated. This form will be signed by a Sponsor representative and the Investigator. A copy of the form will be filed in the site's regulatory binder and in the Sponsor's files.

14 STATISTICAL METHODS AND CONSIDERATIONS

Prior to the analysis of the final study data, a detailed Statistical Analysis Plan (SAP) will be written describing all analyses that will be performed. The SAP will contain any modifications to the analysis plan described below.

14.1 Data Sets Analyzed

All participants who are enrolled, complete a baseline assessment, are randomized, and, for the intervention group, agree to receive GI payments will be included in the modified intention-to-treat analyses. The primary dataset used will be data prospectively collected by the study team via the use of survey instruments and structured interviews as outlined here. We will obtain complementary administrative data on housing status, housing assistance, housing service use, social service use, and health care service use from the Santa Clara Office of Supportive Housing (Homeless Management Information System), Santa Clara Valley Medical Center Hospital & Clinics (Santa Valley Medical Center HealthLink), Santa Clara County Public Health, County of Santa Clara Social Services Agency (including the Department of Employment and Benefit Services), and from community partners (Destination: Home SV, ¡Sí Se Puede! Collective, Sacred Heart Community Service).

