DURATION OF PARTICIPANT PARTICIPATION AND DURATION OF STUDY	
Participants will be followed for 36 months after enrollment.
 
Follow-up: 36 months (24 concomitant with period over which participants will be receiving guaranteed income, plus an additional 12 months after the end of guaranteed income payments).
 
The total duration of the study is expected to be 48 months. 12 months for participant recruitment and 36 months for final participant follow-up.

CONCOMMITANT INTERVENTIONS	Allowed: Any and all other federal, state, county, and local/community assistance services that are available to participants
EFFICACY EVALUATIONS	
PRIMARY ENDPOINT	Our primary endpoint is number of days experiencing homelessness
SECONDARY ENDPOINTS	
 • Time spent unsheltered and/or in unstable housing; physical, mental, social, financial well-being; use of health care and public assistance/social services
STATISTICS Primary Analysis Plan	We will conduct intention-to-treat analyses to assess our primary endpoint, including difference in numbers of days spent homeless using Poisson regression
Rationale for Number of Participants	Our community partner service organizations have resources to provide guaranteed income assistance to 150 families; we plan for a total of 300 participants to enable enrollment of a control group of equal size.

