2.1 Risk / Benefit Assessment

The main risks of receiving guaranteed income (GI) are the same as the risks that would be incurred by the general population in daily life who experience any increase in overall household income: 1) increased income tax burden; and 2) the potential loss of existing public benefits and assistance among participants. Our community partners have primary responsibility for administering and implementing the guaranteed income intervention, and have developed a comprehensive approach to mitigating these risks, including a) limiting the total annual amount of GI to \$12,000 per year, an amount that is considered a non-taxable gift rather than income by the Internal Revenue Service and therefore would not be subject to income tax; b) negotiating waivers to ensure that GI is exempt from being included in eligibility calculations for Santa Clara County and California state assistance services such that participants will maintain the same eligibility for services they would have in the absence of GI; c) providing individualized benefits counseling during the study enrollment process so that potential participants can make informed decisions about participation prior to enrolling in the study; and d) creating a Hold Harmless fund to reimburse participants for any unanticipated benefits losses. The primary potential benefit of guaranteed income is that it will act to enhance and supplement existing housing and social assistance services and decrease homelessness and improve housing stability, health, and well-being of participants. These potential benefits outweigh the risks to participants.

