8 STUDY INTERVENTIONS

8.1 Method of Assigning Participants to Treatment Groups

Up to 300 eligible participants will be randomly assigned to the guaranteed income group (intervention) or usual care (control group) using a computer-generated randomization scheme developed by the study team. Eligible participants will be referred by the community partners (DHSV and SSPC) to the study team for consent and enrollment into the study prior to randomization. Once participants are enrolled, they will undergo a baseline assessment before being randomly assigned to either the intervention or control group. Randomization will be stratified by referring community partner (DHSV vs SSPC). Group assignments will be known to our community partners at Sacred Heart Community Service, a neutral third community-based organization contracted by DHSV and SSPC to administer and provide support for the guaranteed income intervention; however, the core study team (investigators and core research staff at UCSF) will be blinded to group assignments.

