8.2 Blinding

Due to the objectives of the study, the identity of intervention and control groups will not be known to investigators or core research staff (i.e., the UCSF study team). Due to the nature of the intervention, participants themselves will not be blinded to whether they are

assigned to the intervention arm. Community partners at Sacred Heart Community Service, who are administering the guaranteed income intervention, will also not be blinded to participants' group assignments. The following study procedures will be in place to ensure single-blinded administration of the study intervention:

Randomization will take place using a computer-generated randomization scheme integrated into the REDCap randomization module, after participants are consented and enrolled into the study. The REDCap randomization module allows specification of which study team members are blinded vs unblinded to group assignments. Because our community partners at Sacred Heart Community Service are administering the guaranteed income intervention, they will be unblinded to group assignments out of necessity, and will receive the information on individuals' group assignments via a UCSF data liaison working with the UCSF study team. The remainder of the core UCSF study team, including the PI and all key personnel (other than the biostatistician, the aforementioned data liaison, and a participant notification liaison) will be unaware and blinded to participant group assignments during the conduct of the study. The study blind will be broken on completion of the study and after the study database has been locked.

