10 EVALUATIONS BY VISIT

10.1 Visit/Assessment 1: Baseline Survey Assessment (Month 0)

1. Review the study with the participant (participant's legal representative) and obtain written informed consent and HIPAA authorization and assent, if appropriate.
2. Assign the participant a unique screening number.
3. Record demographic data.
4. Record household composition data (number of household members and children).
5. Administer and record current housing situation and history of homelessness instruments, adapted from the Family Options Study and the California Statewide Survey on Homelessness.
6. Administer and record income and employment survey, adapted from the California Statewide Survey on Homelessness.
7. Record concomitant interventions in terms of receipt of assistance from other housing, social, and economic assistance programs.
8. Administer and record monthly expenditure amounts and categories, adapted from the Survey of Income and Participation.
9. Administer and record Financial Well-Being Scale, adapted from the Consumer Financial Protection Bureau (financial well-being).
10. Administer and record Material Hardship Survey, adapted from the Urban Institute Well-Being and Basic Needs and the Survey of Income and Program Participation (material hardship)
11. Administer and record the USDA Brief Food Security Survey (food security)
12. Administer and record healthcare utilization survey, adapted from the California Statewide Survey on Homelessness
13. Administer and record health conditions and functional status survey, adapted from the California Statewide Survey on Homelessness
14. Administer and record Short-Form 12 v2 (physical health)
15. Administer and record Kessler 6 (psychological health)
16. Administer and record the Generalized Self-Efficacy Scale (self-efficacy)
17. Administer and record the Brief Resilience Scale (resilience)
18. Administer and record the Perceived Stress Scale (perceived stress)

19. Administer and record the Confusion, Hubbub and Order Scale (household chaos)
20. Administer and record the Future Scale (aka the Adult Hope Scale) (agency)
21. Schedule participant for Visit 2 in 180-240 days
22. Randomize participant to study group
23. Connect participant with community partner organization (Sacred Heart Community Service) for further social service assessment and assistance (both control and intervention groups) and orientation/navigation for initiation of guaranteed income payments (intervention group)

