14.3 Analysis of Primary Endpoint

We will conduct modified intention-to-treat analyses to assess our primary endpoint, differences in numbers of days spent homeless using Poisson regression.

Analyses will be adjusted for key demographic and clinical characteristics, including: a) referring organization; b) subtype of homelessness; c) preferred payment disbursement schedule (monthly vs hybrid), as well as for covariates that remain unbalanced across the control and intervention groups after randomization. For missing data, we will use multiple imputation, and will employ the last observation carried forward (LOCF), as a sensitivity analysis to assess the robustness of our multiple imputation approach.

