14.4 Analysis of Secondary Endpoints

We will conduct intention-to-treat analyses to assess our secondary endpoints, using Cox proportional hazards, logistic and linear regression models as appropriate to the endpoint of interest. Analyses will be adjusted for key demographic and clinical characteristics, as well as for covariates that remain unbalanced across the control and intervention groups after randomization. As sensitivity analyses, we will also conduct per protocol analyses for both our primary and secondary endpoint measures. For missing data, we will employ multiple imputation and use the last observation carried forward (LOCF) as a sensitivity analysis to assess the robustness of the LOCF approach.

For our qualitative assessments, we will use a thematic approach with simultaneous data collection and analysis based on modified grounded theory methodologies. We will review interview transcripts and initial analytic memos to develop a preliminary codebook, code transcripts and iteratively discuss with the study team to add or revise existing codes, have two reviewers independently review transcripts and conduct coding, and hold regular study team meetings to discuss emergent themes until reaching consensus.

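### The primary analysis set drops randomised families who do not agree to payments, in the intervention arm only, and the synopsis calls the same analysis intention-to-treat

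*Protocol*

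**What the plan says.** Section 14.1 (Data Sets Analyzed) admits participants who have enrolled, have a baseline assessment, "are randomized, and, for the intervention group, agree to receive GI payments will be included in the modified intention-to-treat analyses". Section 14.3 then makes this the primary analysis: "We will conduct modified intention-to-treat analyses to assess our primary endpoint".

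Two other places use a different label:

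- Synopsis, Statistics, for the same Poisson analysis of days homeless: "We will conduct intention-to-treat analyses to assess our primary endpoint".
- Section 14.4: "We will conduct intention-to-treat analyses to assess our secondary endpoints".

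Section 14.1 defines no intention-to-treat set. The only alternative set planned is the per-protocol sensitivity analysis in section 14.4.

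On the order of events, section 8.1 says of enrolled participants that "they will undergo a baseline assessment before being randomly assigned to either the intervention or control group". Section 8.2 says that "participants themselves will not be blinded to whether they are" in the intervention arm. In section 10.1, randomisation is item 22. The contact with the partner organisation that leads to the start of payments is item 23, and the payment part of it is for the intervention group only.

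**The concern.** A condition that only one arm has to meet, and that is met after allocation, undoes what randomisation provides. A family that would turn down payments stays in the analysis if allocated to control and leaves it if allocated to guaranteed income. The intervention arm becomes a selected group, while the control arm remains a mixture of would-be accepters and would-be decliners.

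The direction of the resulting bias is unknown. If decliners would have had more homeless days than accepters, removing them makes guaranteed income look better than it is. If they would have had fewer, removing them hides a benefit.

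Nothing else planned repairs this:

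- Adjustment for observed imbalance (section 14.3) cannot remove selection on unmeasured factors.
- Multiple imputation fills in missing values for families in the set; it does not bring back families left out of it.
- The per-protocol analysis does not restore the decliners.

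The labels matter too. A reader of the synopsis would take the primary result to cover everyone randomised. Whether primary and secondary endpoints are analysed in the same families is unclear.

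**Working it through.** **When agreement happens.** The protocol does not state the moment. The clause applies only to the intervention group, which exists only once allocation is made. A condition settled for everyone before randomisation would bind both arms and would need no such wording. With sections 8.1, 8.2 and 10.1, the natural reading is a condition that follows randomisation and applies to one arm.

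**The plan's own figures.** Inputs from section 14.6: two-sided 0.05, SD 74.0, overall mean 52.3 days, 150 per arm (110 after 27% dropout), target reductions of 24.0 and 28.0 days. Detectable difference = (1.960 + 0.842) × 74 × √(2/n).

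- n = 150: SE = 8.54, difference 23.9 days; power for 24.0 days is 80.2%.
- n = 110: SE = 9.98, difference 28.0 days; power for 28.0 days is 80.1%.

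Both stated figures reproduce. They make no separate allowance for families excluded for not agreeing to payments.

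**Bias from the exclusion.** Two assumptions are needed, as the protocol gives neither figure: *r*, the fraction of the intervention arm that declines, and *D*, the difference in mean homeless days between decliners and accepters. I use D = 37 to 74 days (0.5 to 1 SD) and no true effect, in a two-sample normal comparison as in section 14.6.

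- Bias = r × D
- SE = 74 × √(1/[150(1 − r)] + 1/150)
- Type I error = Φ(−1.96 + bias/SE) + Φ(−1.96 − bias/SE)

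| r | families (of 150) | SE | bias, days | type I error |
|---|---|---|---|---|
| 2% | 3 | 8.59 | 0.7 to 1.5 | 5.1% to 5.3% |
| 5% | 7 to 8 | 8.66 | 1.9 to 3.7 | 5.5% to 7.1% |
| 10% | 15 | 8.78 | 3.7 to 7.4 | 7.1% to 13.5% |

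At 10%, the bias is 3.7/24.0 = 15% to 7.4/24.0 = 31% of the target effect. With D = 0 there is no bias.

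**Limits on D.** Days cannot be negative. The 74-day end therefore requires decliners to be the worse-off group: at r = 10% and overall mean 52.3, accepters average 52.3 − 7.4 = 44.9 days and decliners 44.9 + 74 = 118.9. In the other direction the extreme is decliners at zero days. Accepters then average 52.3/0.9 = 58.1, the bias is 0.1 × 58.1 = 5.8 days against guaranteed income, and the type I error is 10.2%.

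**With dropout.** At 110 per arm the bias in days is unchanged, but the larger SE lowers the type I error: 5.4% to 6.5% at r = 5%, and 6.5% to 11.2% at r = 10%.

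**The case against.** The strongest counter-argument is that refusals may be close to nil. The offer is $24,000 of unconditional cash, and section 2.1 describes waivers, a fund to make good lost benefits, and "providing individualized benefits counseling during the study enrollment process". At 2% declining the distortion is negligible. The 10% row with decliners a full SD worse has no support in the protocol. This is fair, and it limits what can be said about size. It does not make the rule sound: a primary analysis set should not rely on exclusions turning out rare and uninformative when an all-randomised set needs no such luck.

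Second, the timing of agreement is inferred. Section 14.3 adjusts for preferred disbursement schedule, which might mean that some payment preference is asked of everyone before allocation. That lowers certainty slightly, but the wording of section 14.1 still imposes its condition on one arm only.

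Third, the calculation is a normal two-sample model, while the planned analysis is an adjusted Poisson regression, and the main table ignores dropout. Both are true. The figures are illustrative, and the 110-per-arm results are given above.

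Fourth, intention-to-treat in section 14.4 has a plain meaning, and set definitions often come in the SAP. That part is minor. But section 14.1 does not leave the primary set open for the SAP; it fixes it.

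**Conclusion.** The concern holds. Section 14.1 sets an arm-specific exclusion of randomised families, section 14.3 makes that set primary, and the synopsis describes the same analysis differently. Following the plan as written breaks the randomised comparison for the primary endpoint, and no planned analysis of that endpoint covers all randomised families.

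The fault in the rule is clear; the size of its effect is not. Under the assumed refusal rates of 2% to 10% it ranges from under one day to about seven days of bias, in either direction within the limits shown. It should be corrected before analysis, and preferably while decliners can still be surveyed, because outcomes not collected from them cannot easily be recovered later.

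**What to change.** - In section 14.1, delete the clause requiring agreement to payments. Define the primary set as all enrolled participants with a baseline assessment who were randomised, analysed in the arm assigned, whether or not they accept payments.
- Replace modified intention-to-treat with intention-to-treat in sections 14.1 and 14.3, so that they agree with the synopsis and section 14.4.
- Keep the payment-accepting set as a named sensitivity analysis, distinct from the per-protocol analysis in section 14.4.
- State that decliners are invited to the same scheduled surveys. Section 12.1 already encourages this for families who discontinue.

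The disbursement-schedule covariate in section 14.3 is not a new obstacle. Controls receive no payments either, so a rule is needed for them in any case, and the same rule can serve decliners.

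**Cost.** The change is one of wording, plus survey follow-up of a group that has already consented. There is some dilution. If decliners get no effect, the expected difference is 24.0 × (1 − r), with SE 8.54:

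| r | expected difference, days | power, all randomised | power, accepters only |
|---|---|---|---|
| 0% | 24.0 | 80.2% | 80.2% |
| 2% | 23.5 | 78.6% | 79.8% |
| 5% | 22.8 | 76.1% | 79.2% |
| 10% | 21.6 | 71.5% | 78.0% |

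The last column uses the SEs from the bias table and is valid only if there is no selection bias. If refusals are as rare as the objection supposes, the loss of power is small as well.

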14.2 Demographic and Baseline Characteristics

We will summarize the following demographic variables and characteristics at baseline by group assignment: age, gender, race/ethnicity, education, housing status, housing quality/condition, employment, income, financial well-being, material hardship, food security, household composition, health conditions, functional status, healthcare utilization, social service utilization, agency, self-efficacy, perceived stress, household environment.

14.3 Analysis of Primary Endpoint

We will conduct modified intention-to-treat analyses to assess our primary endpoint, differences in numbers of days spent homeless using Poisson regression.

Analyses will be adjusted for key demographic and clinical characteristics, including: a) referring organization; b) subtype of homelessness; c) preferred payment disbursement schedule (monthly vs hybrid), as well as for covariates that remain unbalanced across the control and intervention groups after randomization. For missing data, we will use multiple imputation, and will employ the last observation carried forward (LOCF), as a sensitivity analysis to assess the robustness of our multiple imputation approach.

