14.6 Sample Size and Randomization

Up to 300 eligible participants will be randomly assigned to the guaranteed income group (intervention) or usual care (control group) using a computer-generated randomization scheme developed by the study team. Eligible participants will be referred by the community partners to the study team for consent and enrollment into the study prior to randomization. Once participants are enrolled, they will be randomly assigned to either the intervention or control group. Group assignments will be known to our community partners, who are administering the guaranteed income intervention; however, the study team (investigators and research staff) will be blinded to group assignments.

For our primary endpoint, number of days experiencing homelessness, given our sample size of 300 with 150 participants in each arm, we estimate that we will have 80% power at a two-sided significance level of 0.05 to detect a mean reduction of 24.0 days in the intervention group, assuming a mean of 52.3 ± 74.0 days experiencing homelessness from prior studies. Allowing for a 27% dropout rate as estimated from prior studies (for a total of sample size of 220 participants with 110 families in each arm), we will still have 80% power at a two-sided significance level of 0.05 to detect a mean reduction of 28.0 days in the intervention group.

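### The primary analysis is named as plain Poisson regression, but the planning figures (52.3 ± 74.0 days) imply a variance about 105 times the mean; with default standard errors the 5% test rejects a true null roughly 20% to 85% of the time

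*Protocol*

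**What the plan says.** Section 14.3 specifies a modified intention-to-treat comparison of "differences in numbers of days spent homeless using Poisson regression", adjusted for referring organization, subtype of homelessness, preferred payment schedule and unbalanced covariates. The primary analysis entry of the synopsis names the same model: "including difference in numbers of days spent homeless using Poisson regression". Neither place, nor any other in the protocol, mentions overdispersion, a scale parameter, robust or sandwich standard errors, a negative binomial model or a bootstrap.

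On incomplete outcomes, section 14.3 says "For missing data, we will use multiple imputation". It gives no imputation model and no number of imputations.

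The sample size (section 14.6, repeated in 5.1) is justified "assuming a mean of 52.3 ± 74.0 days experiencing homelessness from prior studies". The period those days cover is not stated. Section 14 promises a detailed SAP before the final analysis and adds: "The SAP will contain any modifications to the analysis plan described below".

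**The concern.** A Poisson model has one parameter for both mean and variance. If days homeless vary far more between families than a Poisson count would, the estimated rate ratio is still usable, but its default standard error is not: it ignores most of the real variation.

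The protocol's own figures say the variation is far larger. The sample size rests on SD 74.0, while the default inference of the named model implies an SD of √52.3 = 7.2. The two sections therefore assume incompatible variances for the same endpoint. If the analysis is run as named with default standard errors, the primary p-value and confidence interval are invalid, and chance differences of a couple of days would be declared significant.

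**Working it through.** **Inputs.** Mean 52.3 and SD 74.0 days, 150 per arm, two-sided 5%, 80% power, and 27% dropout leaving 110 per arm (all section 14.6); Poisson regression and multiple imputation (section 14.3).

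**1. Reproduce the plan's power.** Section 14.6 claims "80% power at a two-sided significance level of 0.05 to detect a mean reduction of 24.0 days". For a two-sample comparison of means, detectable difference = (1.960 + 0.842) × SD × √(2/n).
- n = 150: 2.802 × 74.0 × √(2/150) = 23.9 days; power for 24.0 days is 80.2%.
- n = 110: 2.802 × 74.0 × √(2/110) = 28.0 days; power for 28.0 days is 80.1%.

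Both stated figures reproduce, which confirms that 74.0 is a standard deviation and that planning used the full spread.

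**2. Dispersion.** 74.0² / 52.3 = 5476 / 52.3 = 104.7. Its square root, 10.2, is the factor by which default Poisson standard errors are too small.

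**3. Standard error of the difference in means, 150 per arm.**
- Poisson default: √(2 × 52.3/150) = 0.84 days; significance needs 1.96 × 0.835 = 1.6 days.
- From SD 74.0: 74.0 × √(2/150) = 8.54 days; significance needs 1.96 × 8.545 = 16.7 days.

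**4. Type I error, complete data, default standard errors.** 2 × (1 − Φ(1.96/10.23)) = 84.8%.

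**5. Effect of multiple imputation.** Simulation: 5000 null trials per setting, 150 per arm, negative binomial outcomes matched to 52.3 ± 74.0, unadjusted log-link Poisson regression, Rubin's rules. Assumptions not in the protocol: the whole outcome missing completely at random (40 or 15 per arm, about 27% or 10%), imputation within arm, and 5 or 20 imputations. With complete data the simulated error was 85.2% with default standard errors and 5.5% with a sandwich variance. With imputation (5 / 20 imputations):

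| Imputation of days | Default SE, 27% missing | Default SE, 10% missing | Sandwich, 27% | Sandwich, 10% |
|---|---|---|---|---|
| Hot-deck | 22.6% / 30.1% | 42.4% / 50.0% | 5.7% / 6.3% | 5.6% / 5.6% |
| Normal draws | 20.4% / 28.3% | 39.3% / 50.9% | 5.4% / 5.7% | 4.8% / 5.7% |
| Negative binomial draws | 20.8% / 29.3% | 42.6% / 51.3% | 5.8% / 6.1% | 5.9% / 5.5% |
| Poisson draws | 84.4% / 84.3% | 85.2% / 85.2% | 16.8% / 15.6% | 8.7% / 8.5% |

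Imputed values with the real spread differ between imputations, and that between-imputation variance widens the pooled standard error. It depends on how much is missing and does not correct the model. Poisson draws carry almost no spread, so they leave the default error unchanged and also weaken the sandwich.

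A repeat with 1500 to 3000 trials per setting, including a zero-inflated outcome, agreed. Default standard errors gave 86% on complete data, 21% to 31% at 27% missing with spread-preserving imputation, and 83% to 85% with Poisson draws.

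**6. Sensitivity (complete data, default standard errors; the changed inputs are assumptions).**
- Covariates explain half the variance: dispersion 52.4, error 79%. Three quarters: 26.2, error 70%.
- Mean and SD both halved for another time window: 52.4, error 79%. Both doubled: 209.4, error 89%.
- Dispersion of only 5: error 38%.

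**The case against.** The strongest reply is that the protocol names a regression family and is silent on its variance estimator, a detail usually left to the SAP. Section 14 promises a SAP covering every analysis, and adding a sandwich variance there would complete section 14.3 without contradicting it. Because planning used SD 74.0, the authors clearly knew the spread and may have meant inference that reflects it.

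Part of this stands. The text does not exclude a robust variance, so the error rates describe the method as written, not necessarily the final analysis. But the primary model was not left open. It is named twice, its standard inference contradicts the protocol's own SD, and nothing in the text points away from the default. Knowing the spread at the planning stage makes the mismatch plainer; it does not remove it. A variance estimator left unsaid can also be settled late, and section 8.2 leaves the biostatistician unblinded.

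A second reply is that the lower rates depend on assumed missingness. That is true. Repeated surveys, a withdrawal assessment and administrative housing data mean many dropouts will supply partial outcomes, and the simulations are unadjusted. Less missing information, however, moves the default-variance error up (39% to 51% at 10% missing with spread-preserving imputation). Covariate adjustment leaves it far above 5%.

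Third, quasi-Poisson, negative binomial or bootstrap inference would also address overdispersion. That is correct; the sandwich is simply the smallest change to the named model.

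**Conclusion.** The concern holds. The ratio of 104.7 and the complete-data error of about 85% follow directly from the protocol's figures, given default standard errors. The 20% to 85% range for incomplete data also rests on the assumed imputation models, 5 or 20 imputations and whole-outcome data missing completely at random. Its low end needs 27% missing, few imputations and imputed values with realistic spread. A longer window with mean and SD both doubled would exceed the range (89%). Every default-variance setting examined at the planning mean and SD gives at least four times the nominal 5%. As this concerns the validity of the primary test, it must be corrected before the analysis.

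**What to change.** In section 14.3 and the synopsis, state that the primary analysis is log-link Poisson regression with robust (sandwich) standard errors, computed in each imputed data set and then pooled, and that the primary p-value and confidence interval rest on these. Add that the imputation model for days must not assume variance equal to the mean, so no Poisson draws. The second sentence is needed: with Poisson draws, even the sandwich leaves an error of 16% to 17% at 27% missing.

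The cost is two sentences in the protocol or SAP and one software option. Data collection does not change, and neither does the sample size, which already uses SD 74.0. Intervals will be wider than under the default, and correctly so.
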